## **PROCEDURES STUDIED**

Patients referred for coronary angiography for revascularization are those diagnosed with acute coronary disease (Acute Coronary Syndrome with or without ST segment elevation) or chronic (silent myocardial ischemia, angina).

During coronary angiography, significant lesions are those for which the percentage of stenosis in relation to the reference diameter is  $\geq 50\text{-}70\%$ .

[figure not shown]
In case of angiographic doubt as to the significance of a lesion, an FFR (Fractional Flow Reserve) can be performed. A value less than or equal to 0.80 is thus in favor of a hemodynamically significant lesion.

Depending on the terrain, the number and the characteristics of the lesions, the patient is offered a strategy of surgical revascularization by bypass or interventional by angioplasty.

When the interventional strategy is chosen, the angioplasty of one or more lesions can be performed in one or more stages using stents (generally active) and/or active balloons.

The choice between stenting (active/naked) and active balloon is based on the following criteria:

- Active stenting:
  - hemodynamic instability, malignant ventricular hyperexcitability (VT, VF), plurivessel with altered LVEF,
  - extensive or sub-occlusive type C, D or E dissection or persistence of  $\geq 50\%$  stenosis after predilation.
- Active balloon: residual stenosis  $\leq 30\%$  and absence of extensive or sub-occlusive type C, D or E dissection after predilation(14), patient at risk of hemorrhage.
- Naked stenting: extensive or occlusive dissection after active balloon,

**Figure 1:** diagram of the strategy of revascularization by angioplasty.

\* In case of haemodynamic/rhythmic instability; FFR: Fractional Flow Reserve

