## EVALUATION CRITERIA

The primary endpoint is a composite endpoint of major adverse cardiac events defined as death, nonfatal myocardial infarction (MI), nonfatal stroke (stroke), and target lesion revascularization (TLR) within 12 months then 36 months following the intervention.

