#### **1.3. STATISTICAL METHODS USED**

The parameters collected are presented in tables with descriptive statistics for the total population and for the sub-populations defined by the size of the vessels (small vessels / large vessels) or the procedure used (active stent[s] / stent [s] and balloon[s] active[s] / balloon[s] active[s]), according to the following modalities:

- For quantitative variables: the mean and the standard deviation or the median, the minimum and the maximum
- For qualitative variables: the number, percentages and 95% confidence interval, for each of the modalities of the variable (excluding missing data in the denominator).

The MACE rate will correspond to the ratio of the number of patients having had one or more MACE to the total number of patients for whom the follow-up was carried out at 12 months.then at 36 months.

To compare the sub-populations, the analyzes test the null hypothesis of equality of means for the quantitative variables and of homogeneity of the populations for the qualitative variables:

- For the quantitative variables, after checking the equality of the variances and the normal distribution of the values, the Student test is used. In case of inequality of variances or non-Gaussian distribution, a non-parametric Mann-Whitney/Wilcoxon test is used.
- For qualitative variables, a chi-square test is carried out or a Fisher test in the case of small numbers.

The study of risk factors for MACE is carried out by bivariate analysis. Odds ratios and 95% confidence intervals are calculated.

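### The MACE comparison across device classes is open to confounding by the number of treated lesions, and no lesion-level TLR analysis is specified

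*Combined protocol and SAP*

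**What the plan says.** All references are to the combined protocol and SAP.

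- **Unit of the rate.** Section 1.3 (Statistical methods used) counts each patient once, as "the ratio of the number of patients having had one or more MACE to the total number of patients" with follow-up, at 12 and then 36 months.
- **Endpoint.** Evaluation Criteria lists death, nonfatal MI, nonfatal stroke and "target lesion revascularization (TLR) within 12 months then 36 months following the intervention". The first three happen to a patient; TLR happens to a lesion.
- **Classes.** Section 1.3 sorts patients by procedure into three groups: active stents, stents together with active balloons, and active balloons.
- **Lesions per patient.** Procedures Studied states that "the angioplasty of one or more lesions can be performed in one or more stages using stents (generally active) and/or active balloons". It also lists "Naked stenting: extensive or occlusive dissection after active balloon", so a single lesion can receive both devices.
- **Tests.** Section 1.3: "For qualitative variables, a chi-square test is carried out or a Fisher test in the case of small numbers". It adds: "The study of risk factors for MACE is carried out by bivariate analysis", reported as odds ratios with 95% confidence intervals.
- **Event detail.** Under Follow-up Visits, the patient's cardiologist is contacted for details of any MACE. The fields to be recorded are not listed.

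I found no adjustment for the number of lesions, no lesion-level analysis, and no rule linking a TLR to the device used on the lesion that failed.

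**The concern.** Several of the device-selection criteria in Procedures Studied are findings at the lesion: residual stenosis and dissection after predilation. Device is thus often chosen per lesion but analysed per patient. A patient whose lesions received different devices has to fall in the mixed class, while a single-device class can also hold patients with one lesion and one device. Each extra lesion is another chance of TLR, so two classes with different lesion counts can have different MACE rates even when stents and balloons perform identically.

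This matters because the stated benefit of the study is to confirm or reject the hospital's care algorithm, and that algorithm chooses between stent and balloon. TLR is the MACE component most directly tied to the device, yet it is not examined at the level where the device is used. The small/large vessel split has the same unit problem, since one patient can have lesions in both.

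**Working it through.** **The plan's own figure.** Study Size Calculation gives 1000 patients as 80% of the 1,252 treated in 2017: 0.80 × 1,252 = 1,001.6, which reproduces. It is a feasibility count, with no expected MACE rate, class sizes or lesions per patient. Every input below is therefore an assumption.

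**Model with identical devices.** Let o be the patient's risk of non-TLR MACE, t the TLR risk per lesion whatever the device, and L the number of treated lesions. Assuming independence,

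MACE = 1 − (1 − o)(1 − t)^L.

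**Inputs (assumed).** o = 6%; t = 2%, 4% or 6%; single-device class 70% one lesion and 30% two lesions. The lesion mix of the mixed class is varied, because it drives the result.

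**Step 1: MACE by lesion count.**

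| t | 1 lesion | 2 lesions | 3 lesions |
|---|---|---|---|
| 2% | 7.9% | 9.7% | 11.5% |
| 4% | 9.8% | 13.4% | 16.8% |
| 6% | 11.6% | 16.9% | 21.9% |

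For example, t = 4% with two lesions: 1 − 0.94 × 0.96² = 13.4%.

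**Step 2: MACE by class.** At t = 4%, the single-device class has 0.7 × 9.76 + 0.3 × 13.37 = 10.8%. A mixed class with 80% two and 20% three lesions has 0.8 × 13.37 + 0.2 × 16.83 = 14.1%. The odds ratio is (0.1406/0.8594)/(0.1084/0.8916) = 1.35.

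**Step 3: vary the mixed class.** The single-device rate is 8.4%, 10.8% and 13.2% for t = 2%, 4% and 6%.

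| Mixed class: 1 / 2 / 3 lesions | Mixed MACE at t = 2, 4, 6% | Odds ratio |
|---|---|---|
| 0 / 80 / 20% | 10.1, 14.1, 17.9% | 1.22, 1.35, 1.43 |
| 50 / 40 / 10% | 9.0, 11.9, 14.8% | 1.07, 1.11, 1.14 |
| 70 / 30 / 0% (equal mixes) | 8.4, 10.8, 13.2% | 1.00 |
| 90 / 10 / 0% | 8.1, 10.1, 12.2% | 0.95, 0.93, 0.91 |

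**Step 4: effect on the test.** With an assumed 500 single-device and 200 mixed patients, and a two-sided 5% test of these two classes (normal approximation), the chance of a significant result with identical devices is 12%, 23% and 36% in the first row. It is 6%, 7% and 9% in the second, and the nominal 5% with equal mixes.

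**The case against.** The strongest case on the other side has four parts.

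1. **The class definition requires two devices, not two lesions.** A reader might infer that the mixed class consists largely of multi-lesion patients by construction and must therefore show more MACE. The documents do not support that. A bare stent after an active balloon puts a one-lesion patient in the mixed class, and the single-device classes are worded to allow several stents or several balloons. No lesion distribution is given. This stands: the excess is conditional, and can be nil or reversed.

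2. **Attribution may be possible.** A reader might infer that TLRs in the mixed class cannot be attributed to a device. The cardiologist's event detail, the hospital record and the CardioReport inclusion data may allow it where different lesions received different devices. What stands is that the plan does not specify attribution. Where one lesion received both devices, a lesion-level analysis cannot separate them either.

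3. **The only stated objective is the overall MACE rate, read against the literature.** Counting each patient once is a valid measure for that. The mixed class also validly describes patients treated with a combined strategy, so it is not uninformative. This stands, but section 1.3 does plan to test the classes against each other.

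4. **Lesion count is one confounder among several.** Devices are chosen by instability, LVEF, dissection, residual stenosis and bleeding risk. Handling lesion count will not make the device comparison fair. This also stands, and the report should say so.

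**Conclusion.** The concern holds in a limited form. The planned patient-level MACE comparison across device classes is open to confounding by the number of treated lesions, and the plan neither accounts for lesion count nor analyses TLR by the device on the lesion.

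Over the assumed range, lesion count alone gives an odds ratio for mixed versus single-device anywhere from 0.91 to 1.43. The upper part, 1.22-1.43, needs a mixed class with no one-lesion patients. These figures assume independent lesions, equal TLR risk for both devices, and inputs that the documents do not supply. They show what could happen; they do not estimate what will. The overall MACE rate is not affected. This is an improvement that should be made to a secondary comparison, not a flaw in the primary result.

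**What to change.** - Keep patient-level MACE as the primary rate.
- On the event record already sought from the cardiologist, add which index lesion was revascularized and which device it had received.
- Add TLR per treated lesion, classified by what that lesion received (stent only, active balloon only, both), with standard errors clustered by patient (GEE).
- Report lesions per patient in each device class, and MACE by class separately for one-lesion and multi-lesion patients. Do not interpret the mixed class against the others without that split.
- State that confounding by the device-selection criteria in Procedures Studied remains after these steps.

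The cost is an added entry on the event record, one clustered analysis and slightly more data linkage, with no new patient contact. It assumes that lesion-level device data are available in CardioReport or the hospital record, which should be checked first.

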STATISTICAL ANALYSIS OF DATA	The parameters collected are presented in tables containing descriptive and comparative statistics (total population; small vessel/large vessel subpopulations; stent[s]/stent[s] and active balloon[s]/active balloons subpopulations assets]). The MACE rate corresponds to the ratio of the number of patients who had one or more MACE to the total number of patients for whom the follow-up was carried out at 12 monthsthen to36month. The study of risk factors for MACE is carried out by bivariate analysis.
EXPECTED BENEFITS	The results of this study will make it possible to validate or not the algorithm of care applied to the hospital of La Rochelle. The results will be communicated to the Coronary Atheroma and Interventional Cardiology Group (GACI).

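### The device comparison has three classes, but the plan names only two-sample tests for quantitative variables, so its own null hypothesis cannot be tested as written

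*Combined protocol and SAP*

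**What the plan says.** The statistical row of the Summary of Research announces comparison as well as description: "The parameters collected are presented in tables containing descriptive and comparative statistics". Section 1.3 (Statistical Methods Used) then defines two ways of splitting the patients.

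- By vessel size, two classes: "the sub-populations defined by the size of the vessels (small vessels / large vessels".
- By procedure, three classes: "the procedure used (active stent[s] / stent [s] and balloon[s] active[s] / balloon[s] active[s". The Summary gives the same three-way split.

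One set of rules covers both splits. The hypotheses are set out as follows: "the analyzes test the null hypothesis of equality of means for the quantitative variables and of homogeneity of the populations for the qualitative variables". For quantitative variables the parametric choice is given by "For the quantitative variables, after checking the equality of the variances and the normal distribution of the values, the Student test is used", and the alternative by "In case of inequality of variances or non-Gaussian distribution, a non-parametric Mann-Whitney/Wilcoxon test is used". For categorical variables the rule is "For qualitative variables, a chi-square test is carried out or a Fisher test in the case of small numbers".

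Neither document section names a test for more than two groups on a quantitative variable. Neither gives a rule for pairwise comparisons, a correction for multiple tests, or a significance level.

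**The concern.** The Student and Mann-Whitney/Wilcoxon tests fit the vessel-size split. They do not fit the procedure split, which the same paragraph covers without distinction. The null hypothesis stated for quantitative variables, applied to three device classes, has no matching test in the plan. The categorical rule has no such gap, because a chi-square or Fisher test accepts three groups in one table.

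The analyst must therefore improvise, possibly after seeing the data: three pairwise tests, two contrasts against a reference class, merged classes, or an unplanned overall test. These choices have different error rates. The most direct use of the named tests, three uncorrected pairwise comparisons, flags differences too often and would hold quantitative rows to a looser standard than categorical rows in the same table.

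Device choice is not randomised (Procedures Studied section), so these tables are where a reader looks to see how the device groups differ.

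**Working it through.** **The plan's own figure.** The only planning number is the study size (Study Size Calculation). 0.80 × 1,252 = 1,001.6, against 1,000 stated; 1,000 / 1,252 = 79.9%. The figure reproduces. The plan gives no error rate to reproduce.

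**Inputs.**
- Procedure classes: 3 (section 1.3 and Summary).
- Total patients: 1,000 (Study Size Calculation).
- Significance level: not stated. Assumed two-sided 5%, suggested only by the 95% confidence intervals in section 1.3.
- Split of patients over the classes: not stated, so a range is tried.
- Pairwise use of the two-sample tests: an assumption about how the gap would be filled.

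**Three pairwise tests, equal groups.** With no true difference, the chance that at least one of the three pairwise statistics exceeds 1.96 is a studentized-range probability with k = 3 and large degrees of freedom:

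P(Q > 1.96 × √2) = P(Q > 2.772) = 12.2%.

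**Three pairwise tests, unequal groups.** Let the group means be independent normals with variance 1/nᵢ, and zᵢⱼ = (mᵢ − mⱼ) / √(1/nᵢ + 1/nⱼ). The quantity needed is P(max |zᵢⱼ| > 1.96), here from 1,000,000 draws per split. The last column runs only two contrasts, with the first-listed class as reference.

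| Split of 1,000 | Three pairs | Two contrasts |
|---|---|---|
| 333/333/334 | 12.2% | 9.0% |
| 500/200/300 | 12.1% | 9.5% |
| 700/100/200 | 11.7% | 9.6% |
| 800/100/100 | 11.7% | 9.7% |
| 850/50/100 | 11.6% | 9.7% |
| 600/50/350 | 11.3% | 9.7% |

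In every unequal split the reference is the largest class. A small reference class makes the two contrasts more correlated and lowers the figure. For 600/50/350 with the class of 50 as reference, the correlation is (1/50) / √[(1/600 + 1/50)(1/350 + 1/50)] = 0.90 and the rate is 7.0%.

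**Check with the named tests, no true difference.** Student tests on simulated data gave 12.1% (equal groups) and 12.7% (700/100/200), 5,000 runs each. Mann-Whitney gave 12.2% and 11.2%, 2,000 runs each. The range, about 11–13%, agrees with theory within simulation error.

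**Bounds.** Treating the three tests as independent gives 1 − 0.95³ = 14.3%, and simple addition gives 15%. Both overstate, because each pair of tests shares a group.

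**After the fix.** Rejection by one overall test under no difference:
- one-way ANOVA: 5.1% (equal) and 5.5% (700/100/200);
- Kruskal-Wallis: 4.9% and 4.2%;
- ANOVA with pairwise t tests only if it rejects: 5.1% and 5.5%;
- Welch ANOVA as the gate for Welch t tests: 5.5% and 4.4% (4,000 runs each).

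If one class truly differs and the other two are equal, only one pairwise null is true. Its test is run at 5% at most, so with exactly three groups the gate also holds in that case.

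**The case against.** The strongest reply is that the plan nowhere prescribes three pairwise tests or a 5% level. A reader might infer from the named tests that the plan carries a false-positive rate of about 12% per variable. The documents do not support that as a property of the plan. What they show is an omission: how three classes are compared on a quantitative variable is not stated. The 11–13% is the consequence of one natural way of filling the gap; fewer contrasts would give less. This part of the reply stands.

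Second, the rate applies only to variables that do not differ across all three classes. The Procedures Studied section bases device choice on haemodynamic instability, left ventricular function, dissection, residual stenosis and bleeding risk. For variables tied to those criteria true differences are expected, and a false-positive rate means little. This also stands. It limits how many rows are exposed but does not supply a valid three-group test for any of them.

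Third, the reach is narrow. A reader might infer that the MACE result is compromised. It is not. MACE is binary (Evaluation Criteria), and its comparison across classes falls under chi-square or Fisher. Small versus large vessels is a two-group comparison. The risk-factor analysis compares patients with and without MACE.

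Finally, one might want a count of variables that would be wrongly flagged. The plan lists no variables and gives no number of them, so no such count can be drawn from it.

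None of this rescues the rule as written: "a non-parametric Mann-Whitney/Wilcoxon test is used" and the Student test both remain two-group methods applied to three groups.

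**Conclusion.** The point holds as a mismatch between the stated null hypothesis and the named tests, limited to quantitative variables compared across the three procedure classes. That part rests on the text alone.

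The size is conditional. Assuming two-sided 5%, uncorrected pairwise use and no true difference between classes, the chance of at least one false difference per variable is about 11–13% against a nominal 5%. Two contrasts against the largest class, or against any class if sizes are equal, give about 9–10%, and fewer if the reference class is small. The result changes little over the class sizes tried. No primary or MACE-related conclusion depends on it. The correction is worth making because a suitable test exists, costs almost nothing, and removes a choice that could otherwise be made after seeing the data.

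**What to change.** In section 1.3, and in the matching row of the Summary:

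1. State the significance level and that tests are two-sided, if that is the intention.
2. Restrict the Student and Mann-Whitney/Wilcoxon tests to small versus large vessels.
3. For the three procedure classes, use one overall test per quantitative variable: one-way or Welch ANOVA, or Kruskal-Wallis if the distribution is non-Gaussian. Make pairwise comparisons only if the overall test is significant.

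The cost is a few sentences and slightly fewer nominally significant differences. No data, sample size or procedure changes.

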## GOALS

### 1.1. PRIMARY OBJECTIVE

To assess the safety of angioplasties performed in patients operated on at La Rochelle Hospital, these will be referred to as 12 monthsthen at 36 monthsafter the operation to find out if any major adverse cardiac events (MACE) have occurred since their operation. The MACE rate will thus be determined.

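### Section 1.3 sends Gaussian data with unequal variances to Mann-Whitney under a null of equal means; in unbalanced groups the error rate drifts from an assumed 5%, while Welch's t-test stays close to it.

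*Combined protocol and SAP*

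**What the plan says.** Section 1.3 (Statistical methods used) opens its comparative part by saying that "the analyzes test the null hypothesis of equality of means for the quantitative variables". Student's test is used once equal variances and normality have been checked. Otherwise: "In case of inequality of variances or non-Gaussian distribution, a non-parametric Mann-Whitney/Wilcoxon test is used". Either failure alone is enough to trigger the rank test. Welch's test is not mentioned anywhere.

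The summaries for these variables are given as: "For quantitative variables: the mean and the standard deviation or the median, the minimum and the maximum". The groups compared are small against large vessels (two groups) and the procedure used (three groups: active stents, stents with active balloons, active balloons alone). The Summary of research confirms that testing is intended: "The parameters collected are presented in tables containing descriptive and comparative statistics".

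The plan states no significance level, sidedness, sub-population sizes or SDs.

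**The concern.** Mann-Whitney does not test equality of means, and its null variance assumes that the two distributions are identical. When a variable is Gaussian but its spread differs between groups, that null variance is wrong. In unequal groups the error goes in a predictable direction: too many rejections if the smaller group is more variable, too few if the larger group is.

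Both conditions can arise here. Vessel size is anatomical, and the section on procedures studied has the device chosen on clinical and angiographic criteria, so nothing makes the groups equal in size or spread.

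At stake are the p-values that compare quantitative characteristics between sub-populations. They would point to a difference in means somewhat too often or too rarely.

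**Working it through.** **The plan's own figure.** The study size calculation aims at 80% of the 1,252 patients treated in 2017: 0.80 × 1,252 = 1,001.6, against 1000 stated. This reproduces. The plan gives no error rate for the tests, so there is none to reproduce.

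**Assumptions, because the plan is silent.** Normal data, equal means, two-sided 5%, SD ratios 1.2, 1.5 and 2 in both directions. Splits 500/500, 600/400 and 700/300 of the 1000. The pair 700/150 could arise as two of the three device groups.

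**Closed form for Mann-Whitney.** Let r₁ = s₁²/(s₁²+s₂²) and r₂ = 1 − r₁. Then

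- true Var(U)/(n₁n₂) = 0.25 + (n₂−1)·asin(r₁)/2π + (n₁−1)·asin(r₂)/2π
- variance used by the test: V₀/(n₁n₂) = (n₁+n₂+1)/12
- rejection rate = 2[1 − Φ(1.96·√(V₀/Var(U)))]

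Example: n₁ = 300 with SD 1.5, n₂ = 700 with SD 1. r₁ = 2.25/3.25 = 0.692, so the two arcsine terms are 0.1217 and 0.0498.

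- True: 0.25 + 699 × 0.1217 + 299 × 0.0498 ≈ 100.2
- Used: 1001/12 = 83.4
- √(83.4/100.2) = 0.912; 1.96 × 0.912 = 1.788; rejection rate = 7.4%

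With the SDs exchanged, the true value is 71.4 and the rate is 3.4%.

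**Simulation.** 20,000 trials per setting, Monte Carlo SE about 0.15 points at 5%. Rejection rates in %, for SD ratios 1.2 / 1.5 / 2:

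| Split | More variable group | Mann-Whitney | Welch | Student |
|---|---|---|---|---|
| 600/400 | smaller | 5.8 / 6.5 / 7.7 | 5.3 / 5.1 / 5.1 | 6.1 / 7.1 / 8.3 |
| 600/400 | larger | 4.7 / 4.2 / 4.6 | 5.3 / 4.9 / 5.2 | 4.4 / 3.2 / 2.9 |
| 700/300 | smaller | 6.0 / 7.2 / 9.3 | 5.0 / 5.1 / 5.1 | 6.7 / 9.4 / 12.5 |
| 700/300 | larger | 4.1 / 3.3 / 2.8 | 5.1 / 4.9 / 5.0 | 3.5 / 2.1 / 1.2 |
| 700/150 | smaller | 6.8 / 8.5 / 11.2 | 5.3 / 4.9 / 4.9 | 8.5 / 12.7 / 19.0 |
| 700/150 | larger | 3.8 / 2.3 / 1.2 | 5.0 / 5.0 / 4.9 | 2.7 / 1.2 / 0.2 |

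At 500/500, over all ratios, Mann-Whitney gives 5.2 to 6.1%, and Welch and Student 5.0 to 5.3%. The closed form agrees with the simulated Mann-Whitney column: 6.0 / 7.4 / 9.2 and 4.2 / 3.4 / 2.9 at 700/300; 6.6 / 8.7 / 11.3 and 3.6 / 2.4 / 1.4 at 700/150.

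**The variance check followed by the chosen test.** With a Levene check at 5%, then Student or Mann-Whitney, 700/300 gives 6.0 / 7.2 / 9.3 and 4.0 / 3.3 / 2.8, almost the same as Mann-Whitney alone. The normality check was not simulated; on exactly normal data it would hardly move these rates.

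**A second, independent simulation.** 10,000 trials per setting, SE about 0.2 points, SD ratios 1.25 to 2, splits from 500/500 to 100/900. The pattern is the same. At 200/800 and ratio 2, Mann-Whitney gives 10.8% (smaller group more variable) and 1.5% (larger). Welch runs from 4.3 to 5.4%.

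**Skewed data.** Lognormal with equal means and log-SDs of 0.5 and 0.4: Mann-Whitney rejects in 22 to 25% of trials at 200/800 and about 34% at 500/500, against 4.8 to 5.5% for Welch. The distributions do differ here, so these rejections are errors only if read as statements about means.

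**The case against.** The strongest reply has four parts.

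- **The size is assumed.** The extremes need an SD ratio of 2 and a 700/150 split. At a ratio of 1.2 with 600/400 or 700/300 the rates are 4.1 to 6.0%, and nothing in the documents shows which case applies. This stands and limits the severity.
- **The affected case is narrow.** A variable must pass the normality check, fail the variance check and be compared in unbalanced groups. With groups of several hundred, a formal normality test would send many mildly skewed variables to the rank test anyway, and the fix keeps the rank test for them. This also stands; for those variables only the stated null changes.
- **Restating the null would be enough.** It would not, for this branch. If the null is equality of distributions, the branch is entered only after the variance check has already contradicted it. If the null is that each group is equally likely to give the larger value, it holds exactly in the normal simulations above, yet the rate still leaves 5%.
- **The fallback improves on Student.** In unbalanced groups it does, as the table shows. In balanced groups Student is marginally better. Welch is close to 5% in both.

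It is also fair that the plan does not say whether the three device groups are compared overall or in pairs. Naming three-group tests goes slightly beyond this defect.

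**Conclusion.** The concern holds and is minor. The rule as written pairs a null about means with a test that does not address means and does not keep its level when variances and group sizes both differ. Under the stated assumptions, the Mann-Whitney rate in unbalanced groups runs from 1.2% to 11.2% against a nominal 5%, depending on which group is more variable. Welch stays at 4.9 to 5.3% in the same settings.

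The scope is limited to p-values for quantitative characteristics between sub-populations. The primary objective ("The MACE rate will thus be determined") concerns a proportion and is unaffected. So are the categorical comparisons ("For qualitative variables, a chi-square test is carried out or a Fisher test in the case of small numbers") and the risk-factor estimates ("Odds ratios and 95% confidence intervals are calculated"). No decision on the primary endpoint depends on this point.

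**What to change.** Replace the quantitative rule in section 1.3 with wording such as:

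> Gaussian, equal variances: Student (ANOVA for the three device groups). Gaussian, unequal variances: Welch's t-test (Welch ANOVA for the three device groups). Non-Gaussian: Mann-Whitney (Kruskal-Wallis for the three device groups); the null is equality of distributions, and the median, minimum and maximum are reported with it.

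A significant rank test is then read as a difference in distributions, not in means. The three-group tests are an accompanying clarification, since Student and Mann-Whitney compare only two groups. In 10,000 simulations per setting with unequal SDs (334/333/333 and 600/150/250), Welch ANOVA held 4.6 to 5.2%. Kruskal-Wallis gave 4.9 to 5.7% in balanced groups but 6.3 to 10.0% at 600/150/250, so it is proposed only for non-Gaussian data.

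Keep the chi-square and Fisher tests and the odds ratios as written. The cost is two or three sentences and no new data, because the median, minimum and maximum are already among the planned summaries.

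### MACE risk factors and procedure groups are analysed without adjustment, although device choice follows prognostic criteria; a short prespecified multivariable model and a caveat should be added

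*Combined protocol and SAP*

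**What the plan says.** On risk factors, section 1.3 (statistical methods) says: "The study of risk factors for MACE is carried out by bivariate analysis". Odds ratios with 95% confidence intervals follow, and no adjustment set is named.

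The same section defines sub-populations by vessel size or by "the procedure used (active stent[s] / stent [s] and balloon[s] active[s] / balloon[s] active[s". These are three procedure groups: active stent, stent plus active balloon, and active balloon. They are tested, not only described: "To compare the sub-populations, the analyzes test the null hypothesis of equality of means for the quantitative variables and of homogeneity of the populations", using Student, Mann-Whitney/Wilcoxon, chi-square or Fisher tests. The research summary agrees: "The parameters collected are presented in tables containing descriptive and comparative statistics".

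The section on procedures studied sets out how the device is chosen: "The choice between stenting (active/naked) and active balloon is based on the following criteria". Those for an active stent include "hemodynamic instability, malignant ventricular hyperexcitability (VT, VF), plurivessel with altered LVEF", and also "extensive or sub-occlusive type C, D or E dissection or persistence of" a stenosis of at least 50% after predilation. Those for an active balloon are a residual stenosis of at most 30% with "absence of extensive or sub-occlusive type C, D or E dissection after predilation(14), patient at risk of hemorrhage".

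No section plans a multivariable model, stratification or a propensity score. None warns that the group comparisons may be confounded.

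**The concern.** Device allocation is not random, and the plan writes the allocation rule down. Several of its criteria could plausibly affect death, MI, stroke or target lesion revascularization, which are the components of the primary endpoint. A crude odds ratio for the device, or for a factor tied to its choice, then mixes the effect of the device with the characteristics of the patients selected for it. For factors unrelated to device choice, a bivariate odds ratio is a legitimate description. It cannot show that the factor matters once other factors are taken into account.

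Only secondary results are at stake. They still deserve care, because the plan expects the study to settle whether the hospital's care algorithm is validated and intends to send the results to an interventional cardiology group. That algorithm is largely a rule for choosing a device, so readers will look at the device groups, and nothing in the plan tells them how far those contrasts can be read.

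**Working it through.** **The plan's own figure.** The only figure for study size is a feasibility count: 0.80 × 1,252 = 1,001.6, stated as 1,000. It reproduces. The documents give no expected MACE rate, device-group size, effect size or power, so every input below is assumed.

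**Can crude contrasts mislead materially?** Assume 600 stent and 300 balloon patients (the mixed group is left out for simplicity), no true device effect, and 8% MACE in patients with neither risk. The crude rate in a group is the sum of stratum share × stratum rate. The odds ratio is [p_S/(1−p_S)] / [p_B/(1−p_B)]. The chance of p<0.05 comes from a two-sided pooled z test.

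Worked example: an unstable-type share of 30% (stent) and 5% (balloon), with 25% MACE in that stratum.
- Stent: 0.30×0.25 + 0.70×0.08 = 0.131
- Balloon: 0.05×0.25 + 0.95×0.08 = 0.0885
- OR = (0.131/0.869)/(0.0885/0.9115) = 1.55

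| Unstable-type share, stent vs balloon (MACE in stratum) | Bleeding-risk share, stent vs balloon (MACE in stratum) | Crude rates | Crude OR | P(p<0.05) |
|---|---|---|---|---|
| 40% vs 5% (25%) | none | 0.148 vs 0.0885 | 1.79 | 0.73 |
| 30% vs 5% (25%) | none | 0.131 vs 0.0885 | 1.55 | 0.46 |
| 20% vs 5% (20%) | none | 0.104 vs 0.086 | 1.23 | 0.13 |
| 30% vs 5% (25%) | 5% vs 20% (15%) | 0.1345 vs 0.1025 | 1.36 | 0.27 |
| 30% vs 5% (25%) | 5% vs 20% (20%) | 0.137 vs 0.1125 | 1.25 | 0.17 |
| 30% vs 5% (25%) | 5% vs 40% (20%) | 0.137 vs 0.1365 | 1.00 | 0.05 |
| 10% vs 5% (25%) | 5% vs 40% (20%) | 0.103 vs 0.1365 | 0.73 | 0.33 |

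The sign depends on how the stent criteria (instability) and the balloon criterion (bleeding risk) balance, which the documents do not reveal. A second set of assumptions (low-risk MACE 5% or 10%, high-risk patients at 2 to 3 times that, high-risk shares of 30–40% vs 10–20%) gives crude ORs of 1.09 to 1.61.

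**What can adjustment not reach?** If the predilation result fully determined the device, no stratum would contain both devices and the result could not be adjusted for. With MACE of 10% or 12% after an unfavourable result and 8% after a favourable one, the remaining OR would be (0.10/0.90)/(0.08/0.92) = 1.28 or (0.12/0.88)/(0.08/0.92) = 1.57. Where both devices were used after the same predilation result, that result can enter the model and this part of the bias can be removed.

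**How many terms can be afforded?** A working rule of about 10 events per term is assumed. Device group takes 2 terms. Instability/arrhythmia, multivessel disease with altered LVEF, bleeding risk, predilation result, presentation, age and vessel size take one each: 2 + 7 = 9 terms, or 90 events (9% of 1,000 followed patients).
- 5% MACE in 1,000: 50 events, 5 terms (device, instability/arrhythmia, multivessel disease with altered LVEF, bleeding risk)
- 3% MACE in 1,000: 30 events, 3 terms (device, instability/arrhythmia)

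**The case against.** The strongest reply is that this is a descriptive, non-interventional cohort whose only stated objective is an overall MACE rate, read against the literature. No objective compares devices, and section 1.3 never names the device as a MACE risk factor. The algorithm could be judged by the overall rate alone. This stands, and it limits the point to secondary results. It does not remove it: the risk-factor odds ratios are planned, the procedure groups are tested, and no caveat is given.

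Four stronger readings are tempting, and the documents do not support them.
- A reader might infer that every risk-factor odds ratio is confounded by indication. That applies to the device and to factors linked to its choice; for the rest, the limit is lack of independence.
- A reader might infer that the device contrast is the planned test of the algorithm, or that the bias favours one device. The plan does not say the first, and the criteria pull in opposing directions on the second.
- A reader might infer that a bare stent placed after an active balloon belongs to no procedure group. On a plain reading it falls in the mixed stent-and-balloon group; any doubt may come from translation and needs only confirmation.
- A reader might infer that the predilation result can never be adjusted for. That holds only where it leaves no overlap between devices.

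It is also fair to say that section 1.3 already tabulates the collected parameters by procedure group. That supplies much of an overlap table, if the relevant variables are collected. The documents list no baseline variables, so this is unknown.

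**Conclusion.** The point holds as a worthwhile, inexpensive improvement to the secondary analyses. Three facts in the text support it: risk factors are studied by bivariate odds ratios only, procedure groups are compared without adjustment, and devices are allocated by criteria that plausibly carry prognosis. Neither adjustment nor a warning is planned.

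Its size in this study is unknown. The range of 0.73 to 1.79 for the crude odds ratio, with nominal significance in about 5% to 73% of studies, is an illustration under assumed shares, rates and group sizes. It includes a case with no bias. It shows that material bias is possible in either direction, not that it will occur. The primary MACE rate needs no adjustment and is untouched.

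**What to change.** 1. Keep the bivariate results. Add to section 1.3 one prespecified multivariable logistic model of MACE at 12 months, and the same model at 36 months, limited to about one term per 10 events. Give priority to device group and the recorded device-choice criteria: instability/arrhythmia, multivessel disease with altered LVEF, bleeding risk, and predilation result where both devices were used. Then add presentation, age and vessel size as events allow, with vessel size defined at patient level for patients with several lesions.
2. Tabulate these covariates by device group, marking strata in which only one device was used.
3. State that device contrasts are associational and do not by themselves validate the algorithm.
4. Confirm in one line that a bare stent after an active balloon is counted in the mixed group.

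The cost is SAP wording and some analysis time, with no extra patient contact. The downsides are that availability of the covariates in CardioReport or the hospital record must be confirmed, few events would shorten the model, and confounding remains in strata where only one device was used. If the covariates prove unavailable, the statement in step 3 can still be made and becomes the essential part.
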